8.5.2 Longer Term Analysis for the First Tier of Efficacy Endpoints

1) Overall survival throughout the parent trial and LTE study duration

Kaplan-Meier survival analysis will be performed. The probability of survival will be evaluated at one, three, and five (if there is sufficient follow-up time) years after initial study participation in the parent trial through the completion of the LTE trial.

A Cox regression analysis will be performed with baseline REVEAL Lite 2.0 category score and IPAH/HPAH or Non-IPAH/HPAH category. The hazard ratio and its 95% CI for the pairwise LTE treatment groups will be reported for Group 1 versus Group 4, Group 3, and Group 2 respectively.

2) Change from LTE baseline to post-LTE baseline in continuous effectiveness endpoints

The continuous endpoints measured at multiple timepoints include:

- Change from baseline in NT-proBNP
- Change from baseline in 6MWD
- Change from baseline in REVEAL Lite 2.0 Score
- Change from baseline in QoL emPHasis-10 Questionnaire score
- Change from baseline in Borg dyspnea index

The following analysis described for change from baseline in NT-proBNP will be used for the analysis of the continuous endpoints enumerated above.

The pairwise mean difference in change from LTE baseline among LTE treatment groups will be estimated using a mixed model for repeated measures (MMRM) model where the response is change from LTE baseline in an NT-proBNP at each post-baseline visit for each subject.

The explanatory variables will include:

- Fixed effect factors
 - Visit
 - LTE treatment groups
 - LTE treatment groups by visit interaction
 - IPAH/HPAH or Non-IPAH/HPAH category
- Fixed effect covariates
 - Continuous pre-LTE baseline value
 - Continuous parent trial baseline REVEAL 2.0 score
- Subjects as random effects

Unstructured covariance will be specified. If the fitted model does not converge with unstructured covariance, a simpler covariance will be specified. LSMeans by trial treatment groups and difference in mean change from baseline in NT-proBNP at each visit will be reported. At each post-baseline visit (with focus on Weeks 24, 48 and 72 after LTE entry) the difference in mean change from baseline in NT-proBNP between treatment groups and its 95% CI for the treatment term will be reported. The mean difference in change from LTE baseline between subjects always on the optimal dose will be compared in the following order: 1) always on placebo (Group 4); 2) placebo followed by an active treatment dose (Group 3); 3) always on the non-optimal dose (Group 2). Average treatment effectiveness before and after optimal dose treatment during the LTE will also be presented.

Trends in change from baseline (CFB) will initially be assessed graphically. To obtain a measure of trends using MMRM, visits as continuous variables, and visit by LTE treatment groups interactions will be entered into the model. The coefficient for continuous visit associated for each of the LTE treatment groups indicates the linear trend in change from baseline over visit. A non-linear trend in CFB will be tested by entering visit as quadratic or cubic spline of visit in the model.

3) Maintenance or improvement in WHO Functional Class throughout the LTE

At each post-LTE baseline visit, a subject's status with respect to remaining in or decreasing from the same WHO FC will be recorded. At each post-baseline visit, the proportion of subjects who remain or improve on their baseline WHO FC will be reported by treatment groups. A logistic regression model will be fitted where the response at each visit is whether the subject remains in or improves in WHO FC. The explanatory variables consist of LTE treatment groups, visit, LTE treatment groups by visit, IPA/HPA or non-IPA/HPA category, and continuous LTE baseline REVEAL Lite 2.0 score.

Visits within a subject form a cluster. Estimated proportions by treatment group and visit will be reported. For Week 24 after optimal dose treatment, the log of odds and proportions of subjects who maintain or improve WHO FC and their 95%CI will be reported by treatment groups. Odd ratios (OR) and 95%CI for subjects always on optimal dose (Group 1) relative to those subjects on always on placebo (Group 4) will be reported. OR and 95%CI among subjects always on optimal dose (Group 1) relative to those of subjects on placebo and then active treatment (Group 3) and OR and 95%CI among subjects always on optimal dose (Group 1) relative to those of subjects on non-optimal dose (Group 2) will also be reported.

4) Time to Clinical Worsening

Time to clinical worsening while in the parent trial and LTE will be based on the first occurrence of any of the following events for each subject.

- Death
- Initiation of parenteral prostanoids
- Hospitalization for worsening PAH
- $\geq 15\%$ decline from baseline in 6MWD and accompanied with progression to or continued WHO FC III or IV symptoms

A subject is evaluated for experiencing any of the above components of clinical worsening throughout the parent trial and LTE study period. Time to clinical worsening is the number of days between the earliest occurrence of the clinical worsening component and the date of the first dose in the parent trial. With treatment groups that change over time intervals, event and censoring will be defined within each time interval. A subject who does not experience any of the clinical worsening component throughout a treatment period/interval is censored and is assigned time to worsening status by the end of the interval. Subjects who are lost to follow-up are typically considered censored. Supplemental analyses will be performed where subjects with an unknown clinical worsening event will be considered to

experience the event and the time to clinical worsening status is the last contact with the subject.

The probability of clinical worsening every 24 weeks after the first dose in the parent trial throughout the LTE will be reported, descriptively as well as based on a Cox model for time to clinical worsening while holding covariates at their means.

A Cox model will be fitted to time to clinical worsening with terms for time-varying by treatment dose groups, continuous LTE baseline REVEAL Lite 2.0 score (among those randomized to placebo in Phase 3), continuous parent baseline REVEAL Lite 2.0 score, and IPAH/HPAH or Non-IPAH/HPAH category.

The hazard ratio and its 95% CI for the pairwise treatment dose groups will be reported for:

- Always on the optimal dose (Group 1) versus always on placebo (Group 4)
- Always on the optimal dose (Group 1) versus on placebo followed by an active dose (Group 3)
- Always on the optimal dose (Group 1) versus always on a non-optimal dose (Group 2)

Kaplan-Meier curves by parent trial treatment groups will be generated.

5) Achieving multicomponent clinical improvement will be analyzed as a binary as well as a time to event response throughout the LTE period

a) Binary response throughout LTE period: At each LTE visit, a subject response is set to 1 for achieving multicomponent clinical improvement if he meets all of the following three conditions:

- FC improvement or maintenance of FC II status
- NT-proBNP \geq 30% improvement or $<$ 300 pg/ml
- 6MWD \geq 30 meters improvement

Otherwise, the response value is 0.

A logistic regression model will be fitted to the binary response of achieving multicomponent clinical improvement at each visit. The explanatory variables will include LTE treatment groups categorical visit, LTE treatment groups by visit interaction, continuous LTE baseline REVEAL Lite 2.0 score, continuous parent baseline REVEAL Lite 2.0 score, and IPAH/HPAH or Non-IPAH/HPAH category. The subject's multicomponent clinical improvement status during the parent study may be considered as an explanatory variable. Subjects will be specified as clusters.

b) **Time to Event Response from start to end of the LTE:** Time to achieve multicomponent clinical improvement response is defined as the days since the first

dose that a subject achieves clinical improvement in all 3 components from the start through the end of LTE. The number of days between the date that a subject meets all of the multicomponent improvement parameters and the first LTE dose date is the time to achieving multicomponent improvement. A subject who does not experience multicomponent improvement is censored during the time interval. A subject who is lost to follow-up without recording this multicomponent improvement is censored at the last visit in which the above parameters are recorded. Supplemental analyses will be performed where those lost to follow-up are considered a failure at the time of the lost to follow-up.

The Cox hazard model as described for time to clinical worsening will be implemented for time to multicomponent clinical improvement.

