Figure 1 presents the design schematic of this study.

For Subjects Entering the LTE from the Phase 2b and Intermediate Parts of AV-101-002

For Subjects Entering the LTE from the Phase 3 Part of AV-101-002

- A. Screening/Baseline Visit and procedures for the LTE will be conducted at the Week 24 Visit for AV-101-002.
- B. Once the optimal dose is selected for the parent Phase 3 Part of AV-101-002, subjects who enter the LTE from the Phase 2b Part and the Intermediate Part of AV-101-002 will be transitioned to the optimal dose.
- C. Once the AV-101 optimal dose has been selected, the LTE will no longer be blinded. Subjects enrolled during the Intermediate Part of AV-101-002 that enter the LTE study after the optimal dose is selected will be assigned to that dose upon completion of the Week 24 Visit for AV-101-002.

Target Population: Patients with Group 1 PAH who have successfully completed study AV-101-002.

Duration of Study Drug Treatment: The LTE study will continue until 31 December 2025 or until the Sponsor stops the study.

Diagnosis and Main Eligibility Criteria: For a complete list of study inclusion and exclusion criteria, please refer to [Section 4.1](#) and [4.2](#).

Key Inclusion Criteria:

To be eligible, a participant is required to be or have:

- Consented to participate in the LTE and has successfully completed the placebo-controlled 24-week Study AV-101-002.
- Female subjects of childbearing potential who have agreed to continue to use a highly effective form of contraception during the LTE and for at least 30 days after completing or discontinuing study treatment (highly effective forms of contraception are described in [Section 7.8](#)).

Key Exclusion Criteria:

Subjects meeting any of the following criteria:

- The Investigator believes that it would not be in the best interest of the subject to be included in the LTE e.g., for clinical or social reasons.
- Subjects who were not compliant with study medication in AV-101-002 as assessed by the Investigator.
- Applicable for France only: Persons referred to in Article L1122-2 of the French Public Health Code:
 - Person deprived of liberty by a judicial or administrative decision
 - Person under psychiatric care
 - Person admitted to a health or social institution for purposes other than research
 - Person who is the subject of a legal protection measure (tutelage, guardianship, safeguard of justice)

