3.3 Data Safety Monitoring Board

A DSMB will be utilized in this study to ensure external objective medical and/or statistical review of safety and/or efficacy issues in order to protect the ethical and safety interests of subjects and to protect the scientific validity of the study. The schedule of the analysis plan for DSMB review is described in the charter, which is available upon request.

4 Study Population

The eligibility criteria in [Sections 4.1](#) (Inclusion Criteria) and [4.2](#) (Exclusion Criteria) are designed to enroll only subjects who completed AV-101-002. All relevant medical and nonmedical conditions as well as tolerance to AV-101 should be taken into consideration when deciding whether a subject is suitable for this study.

Prospective approval of protocol deviations to inclusion and exclusion criteria, also known as protocol waivers or exemptions, is not permitted.

Before performing any study assessments that are not part of the subject's routine medical care, including Week 24 assessments from AV-101-002 which will serve as baseline for this study, the Investigator will confirm that the subject has provided written informed consent, as indicated in [Section 9.1.3](#).

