4.1 Inclusion Criteria

For inclusion in the study, all of the following inclusion criteria must be fulfilled:

1. Subjects who have consented to participate.
2. Subjects who have successfully completed the placebo-controlled 24-week study AV-101-002 without a treatment-limiting toxicity resulting in discontinuation of study drug.
3. Female subjects of childbearing potential who have agreed to continue to use a highly effective form of contraception during the LTE and for at least 30 days after completing or discontinuing study treatment (highly effective forms of contraception are described in [Section 7.8](#)).

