8.1 Introduction: Study Design and Analysis Overview

The LTE is a longitudinal study of the long-term safety and effectiveness of PAH patients treated with AV-101 at different dose levels until being transitioned to the optimal dose of AV-101 which is selected after the completion of the Phase 2b Part of Study AV-101-002 (referred to as the parent study). About 370 subjects (with a maximum of 462 subjects) are expected to start the LTE. LTE subjects may be grouped into the following treatment groups:

- **Group 1 – Optimal Dose Treatment:** Subjects treated with the optimal dose throughout the parent trial and throughout their LTE participation.
- **Group 2 – Non-Optimal Dose Active Treatment, then Optimal Dose Treatment:** Subjects treated with active doses not selected as the optimal dose, who eventually will be treated with the optimal dose when this dose is selected.
- **Group 3 – Placebo to Non-Optimal Dose, then Optimal Dose Treatment:** Subjects originally assigned to the placebo arm during the parent trial then re-randomized to the two non-optimal active groups. Later, they will receive the optimal dose when it is selected.
- **Group 4 – Placebo to Optimal Dose Treatment:** Subjects originally assigned to the placebo arm during the parent trial then either re-randomized or switched to optimal dose.

Further characteristics of these LTE treatment groups are described in [Section 8.3](#).

Among the comparisons to consider are:

- 1) LTE levels and trends among subjects always on the optimal dose Group 1 will be compared in order with those of:
 - Group 4: Placebo to optimal dose treatment
 - Group 3: Placebo to non-optimal dose, then optimal dose treatment
 - Group 2: Non-optimal dose active treatment, then optimal dose treatment
- 2) Levels and trends in LTE safety and effectiveness endpoints for subjects always on the optimal dose (Group 1) will be compared to levels and trends during the parent study among these same subjects. This will be done to document whether the effects of the previous optimal dose on subsequent measures of effectiveness and safety while still undergoing treatment persist, improve, plateau, or dip the longer the duration of the optimal treatment.
- 3) Trends in continuous LTE effectiveness endpoints will be assessed separately for continuous dose intensity and continuous relative dose intensity.

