Trends or patterns over time in safety and effectiveness measures will be presented using repeated measures data analysis methods applicable to categorical or continuous data. Time-to-event analyses will be performed using Cox models with time-independent and time-varying covariates, specifically, extent of AV-101 dose intensity as continuous or categorical variables. For time to event data like overall survival, the starting period is the day prior to the first dose in the parent trial. Kaplan-Meier procedures for time -to-event analysis will also be performed.

For longitudinal continuous variables, the shape of the effectiveness trajectory (trends), repeated measures models over time will be fitted to assess whether the effectiveness measure indicates waxing, waning or remaining persistently over time. During the LTE, visits may be grouped into before or after optimal dose is administered. Levels of the LTE effectiveness endpoints before or after optimal dose treatment during the LTE will be reported.

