8.2 Analysis Sets

The following analysis sets will be used to address the specific protocol objectives.

Screened Analysis Set (SAS): The screened analysis set consists of subjects treated at least once in the parent study who signed the informed consent to participate in the LTE study. This is the analysis set for presenting LTE baseline information and the status of subject participation in the LTE study.

Safety (SAF) Analysis Set: The safety analysis set includes all subjects enrolled in the LTE who received at least one dose of treatment during the LTE. This analysis set is the primary analysis set used for all safety summaries.

Full Analysis Set (FAS): The full analysis set includes all subjects enrolled in the LTE who received at least one dose of treatment during the LTE and have at least one post-LTE entry effectiveness measure recorded. This analysis set is the primary analysis set used for all effectiveness analyses.

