8.5 Effectiveness Analyses

Descriptive summary statistics will be reported for each effectiveness endpoint by LTE treatment groups. The FAS will be used as the analysis set. Comparisons of levels in effectiveness endpoints at specific visits (e.g. Week 24 after LTE baseline) among LTE treatment groups will be performed using statistical models applicable to the measurement scale (continuous, categorical, time-to-event). Tests of hypotheses in these models will be performed with two-sided tests at 0.05 significance level, adjusted for multiple comparisons. Effectiveness endpoints among Group 1

subjects will be compared with subjects in Group 4, Group 3, and Group 2. Associated 95% confidence intervals for the difference in outcomes in pairwise treatment comparisons will be presented. Trends in effectiveness endpoints measured over time will be presented graphically by using applicable summary statistics at each time point. If appropriate, statistical tests of the differences in trends may be performed.

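### Overall survival is timed from the first parent-trial dose but analysed only in subjects who reached the extension, so the Kaplan-Meier landmarks are conditional on that and not labelled so

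*Combined protocol and SAP*

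**What the plan says.** Four parts of the protocol together define the survival result.

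- **Clock.** Section 8.1 sets the origin: "For time to event data like overall survival, the starting period is the day prior to the first dose in the parent trial".
- **Landmarks.** Section 8.5.2, item 1, whose title covers both the parent trial and the LTE, says: "The probability of survival will be evaluated at one, three, and five (if there is sufficient follow-up time) years after initial study participation", counted from the parent trial.
- **Analysis set.** Section 8.5 says of the effectiveness analyses: "The FAS will be used as the analysis set". Section 8.2 limits that set to enrolled LTE subjects who "received at least one dose of treatment during the LTE and have at least one post-LTE entry effectiveness measure recorded". The Cox comparisons use Groups 1 to 4, which Section 8.1 introduces with "LTE subjects may be grouped into the following treatment groups".
- **Entry.** Section 4 calls the eligibility criteria "designed to enroll only subjects who completed AV-101-002", and inclusion criterion 2 in Section 4.1 reads: "Subjects who have successfully completed the placebo-controlled 24-week study AV-101-002 without a treatment-limiting toxicity resulting in discontinuation of study drug".

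The widest set in Section 8.2, the Screened Analysis Set, also requires consent to the LTE. Section 8 describes itself as an overview and leaves details to a statistical analysis plan.

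**The concern.** The clock starts about 24 weeks before anyone can join the analysis set. A parent-trial subject who died in that time cannot be in the FAS, so the Kaplan-Meier curve is fixed at 100% over that stretch. The FAS also requires a post-entry effectiveness measure. Unless death counts as one, which is not stated, a subject who dies soon after the first LTE dose without any other measure drops out as well.

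Survival is a listed endpoint (Section 2.2) and the first item in the first tier (Section 8.5.2). The Synopsis says the summaries will go into regulatory submissions and to the DSMB. Someone shown a 1-year or 3-year survival figure dated from parent-trial participation would take it as survival from the start of the parent trial. The 1-, 3- and 5-year landmarks also match registry time points quoted in Section 1.1. No comparison with the registry is planned, but it would be an easy one to make.

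**Working it through.** The plan gives no survival target, event count or parent-trial mortality, so there is no figure of its own to reproduce. The check derives what the estimator targets and then sizes the gap under stated assumptions.

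**1. What is estimated.** Let S(t) be survival from first parent-trial dose. Every FAS subject is alive at about Week 24, so the curve estimates S(t | alive at 24 weeks) = S(t) / S(24 weeks). Each landmark is inflated by 1 / S(24 weeks). This assumes that subjects alive at Week 24 who do not enter the LTE have the same later risk as entrants.

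**2. Inputs.** T = 168 / 365.25 = 0.460 years. The 24-week mortality m is not given; I take 1%, 3% and 5% as assumptions. Two assumptions about the later hazard bracket the result:
- (i) constant hazard: S(y) = (1 - m)^(y/T);
- (ii) 1- and 3-year survival held at the registry's 85% and 68% (Section 1.1), whatever m is.

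In both cases the value shown is S(y) / (1 - m).

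**3. Results (survival from first dose -> value shown, %).**

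| m | 1 y, (i) | 1 y, (ii) | 3 y, (i) | 3 y, (ii) |
|---|---|---|---|---|
| 1% | 97.84 -> 98.83 (+1.0) | 85.0 -> 85.9 (+0.9) | 93.66 -> 94.60 (+0.9) | 68.0 -> 68.7 (+0.7) |
| 3% | 93.59 -> 96.49 (+2.9) | 85.0 -> 87.6 (+2.6) | 81.98 -> 84.52 (+2.5) | 68.0 -> 70.1 (+2.1) |
| 5% | 89.45 -> 94.16 (+4.7) | 85.0 -> 89.5 (+4.5) | 71.57 -> 75.33 (+3.8) | 68.0 -> 71.6 (+3.6) |

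Kaplan-Meier on 1,000,000 simulated exponential times, with administrative censoring uniform on 0.6 to 4.5 years, gave 1-year values of 97.84 against 98.82 (m = 1%), 93.59 against 96.46 (3%) and 89.43 against 94.14 (5%). This confirms the algebra, not the constant hazard.

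**4. Registry illustration.** Nothing in the documents caps m at 5%. With a constant hazard in year 1, the registry's 85% gives S(24 weeks) = 0.85^0.460 = 0.928, so m = 7.2% and the factor is 1 / 0.928 = 1.078. The 1- and 3-year values move from 85% and 68% to 91.6% and 73.3% (+6.6 and +5.3 points). Registry time runs from diagnostic catheterization, so this is an illustration and not an estimate for this trial.

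**5. Effect of the post-entry measure.** If it moves the guaranteed time to the Week 4 clinic visit (28 weeks from first parent dose), the registry illustration becomes 92.8% and 74.2% (+7.7 and +6.2 points).

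**6. Hazard ratios.** No deaths occur in the window in any group, so it adds nothing to the Cox comparison. With a true hazard ratio of 0.60, simulation gave 0.602 in all subjects and 0.601 in those alive at Week 24 with time counted from then.

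**The case against.** The strongest reply is that this is a labelling matter. The restriction to completers is open: it is in the study title, the target population, Section 4, the inclusion criteria and the FAS definition. The study's main objective is safety, no survival target or power is stated, and Section 8 leaves detail to a later plan. Much of this stands. Nothing is concealed, and the correction can go in the analysis plan. But the origin, set and landmarks are already fixed in Section 8, and together they give a conditional probability under a title that promises the parent trial too. That is a stated rule with a wrong absolute reading, not a missing detail.

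A reader might infer more than the documents support:

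- **That the group comparisons are biased.** The event-free window is common to all four groups and does not itself distort the hazard ratios. They do describe LTE entrants only.
- **That first-year mortality would be shown about 45% too low**, since 24 weeks is 46% of a year. This holds only under a constant hazard. With 1-year mortality held at the registry's 15%, the values shown would be 14.1%, 12.4% and 10.5% at m = 1%, 3% and 5%, which is about 6%, 18% and 30% too low.
- **That a 5-year figure will be overstated.** That reading is itself conditional on follow-up. The Synopsis says "The LTE study will continue until 31 December 2025 or until the Sponsor stops the study", so five years would need a first parent dose by 31 December 2020, and the parent trial's start date is not given.
- **That parent-trial deaths occurred.** The documents do not say.

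**Conclusion.** The concern holds for the absolute Kaplan-Meier landmarks only. As planned, they are conditional on completing AV-101-002, receiving an LTE dose and, as the FAS is worded, having a post-entry effectiveness measure. They overstate survival from first parent-trial dose by about 1/S(24 weeks) if any parent-trial subject died before entry. This structure follows from the text and is firm.

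The size is not known. It is zero with no parent-trial deaths. Across the two later-hazard assumptions, the 1-year overstatement is 0.9-1.0 points at 24-week mortality of 1%, 2.6-2.9 at 3% and 4.5-4.7 at 5%; the 3-year overstatement is 0.7-0.9, 2.1-2.5 and 3.6-3.8. These rest on entrants and surviving non-entrants having the same later risk; if non-entrants do worse, the gap is larger. It should be corrected because survival heads the first tier and the remedy is cheap.

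**What to change.** Change Sections 8.1 and 8.5.2, item 1, for overall survival.

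**First, the set.** Analyse survival on the Safety Analysis Set (all LTE-dosed subjects), or state that death counts as a post-entry effectiveness measure. Without this, early LTE deaths can still be lost under either option below.

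**Then one of two options.**
- (a) Time survival from the first LTE dose and restate the landmarks from there. The cost is about 24 fewer weeks of displayed follow-up. The text should note that Groups 1 and 2 have by then had about 24 weeks of AV-101, while Groups 3 and 4 are just starting it.
- (b) Keep the parent-dose origin and state that the probabilities are conditional on completing AV-101-002 and receiving an LTE dose, with the period before entry event-free by design. The cost is one sentence, with no new data.

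If (a) is chosen, confine the new origin to survival. The rule in Section 8.1 is worded for time-to-event data generally, and time to clinical worsening counts parent-period events.

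An estimate from first dose in all subjects treated in AV-101-002 is optional, and possible only if parent-trial vital status exists for those who did not enter; the documents do not say whether it does. Treating LTE subjects as delayed entries would not recover survival over the first 24 weeks.

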8.4 Baseline and Demographics and Subject Study Disposition

With exception of the delayed-start analysis, for both the efficacy and safety analyses, baseline will be defined as the time prior to starting active treatment with AV-101 in either the LTE or the parent study. For Groups 1 and 2, since the subjects start receiving active treatment in the parent study, the baseline will be the values prior to first dose during the parent trial. For Groups 3 and 4, the subjects receive placebo in the parent trial and then receive active treatment in the LTE study, thus, the baseline will be the values prior to the first dose in LTE study.

Demographics and baseline data, medical and surgical history will be summarized using the screened analysis set. These demographics and baseline data will be presented by the LTE treatment groups as described in [Section 8.1](#).

Demographic and baseline data will be summarized using summary statistics of mean, standard deviation, median, lower quartile, upper quartile, min and max for continuous variables and number and percentage of subjects in each category.

Subject treatment status and study participation status will be reported for the safety analysis set. Subjects who completed all LTE assessments and early treatment discontinuation and withdrawal from the study including reasons for treatment or study discontinuation will be reported by LTE treatment groups.

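### Under the plan's general baseline rule, the overall-survival Cox model adjusts Groups 1–2 for a pre-treatment REVEAL Lite 2.0 category but Groups 3–4 for one taken after 24 weeks of placebo

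*Combined protocol and SAP*

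**What the plan says.** Section 8.1 sets the survival clock for all groups: "For time to event data like overall survival, the starting period is the day prior to the first dose in the parent trial". Section 8.5.2 item 1 gives the model: "A Cox regression analysis will be performed with baseline REVEAL Lite 2.0 category score and IPAH/HPAH or Non-IPAH/HPAH category". It then lists the contrasts: "The hazard ratio and its 95% CI for the pairwise LTE treatment groups will be reported for Group 1 versus Group 4", and likewise against Groups 3 and 2.

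Item 1 does not define baseline. Section 8.4 does: "With exception of the delayed-start analysis, for both the efficacy and safety analyses, baseline will be defined as the time prior to starting" active AV-101 in either study. For Groups 1 and 2, "the baseline will be the values prior to first dose during the parent trial". For Groups 3 and 4, which took placebo in the parent trial, "the baseline will be the values prior to the first dose in LTE study". The Statistical Methods part of the synopsis and Section 8.1 take the same line. Overall survival is listed among the first-tier efficacy endpoints, and only the delayed-start analysis is exempt.

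Other models in Section 8.5.2 name their baseline. The MMRM in item 2 uses the parent-trial baseline REVEAL score. The clinical-worsening Cox model in item 4 uses the parent-baseline score together with an LTE-baseline score for subjects on placebo in Phase 3.

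**The concern.** A programmer who applies Section 8.4 to item 1 would build a covariate that means different things in the arms being compared. In Group 1 it is measured before any study drug. In Groups 3 and 4 it is measured after 24 weeks of placebo, when the treatment difference of interest has already operated. REVEAL Lite 2 includes 6MWD, NT-proBNP and WHO functional class (Section 6.6.7), which the drug is meant to change.

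Take two subjects who both enter the parent trial with a score of 7, which is intermediate risk. The Group 4 subject reaches 8 by Week 24 and is coded high risk. The Group 1 subject stays coded intermediate whatever the Week 24 score is. If the Group 4 subject had instead improved to 5, the code would be low risk, again with no counterpart in Group 1.

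Two of the three planned survival hazard ratios are affected.

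**Working it through.** The documents state no survival hazard ratio, event count or power for this model, so there is no plan figure to reproduce. The check is a large-sample simulation of Group 1 versus Group 4.

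**From the documents**
- Three-year registry survival is 68% (Section 1.1), so the average hazard is h0 = −ln(0.68)/3 = 0.129 per year.
- Risk categories are 1–5, 6–7 and 8 or more (Section 6.6.7).
- The FAS contains only LTE-dosed subjects (Section 8.2), so everyone is alive at Week 24.

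**Assumed**
- Parent score S0 has mean 6.5 and SD 2.2. The SD of the 24-week change is 1.5.
- The mean change is d1 in Group 1 and d4 in Group 4.
- The hazard ratio per score point is 1.4 or 1.2.
- Follow-up is 3 years after LTE entry, with 100,000 subjects per group.

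**Model.** After Week 24 the hazard is h0 × exp[b(S24 − 6.5)], where S24 is S0 plus the change and b is the log hazard ratio per point. At equal S0, the groups differ in log hazard by roughly b(d1 − d4). If Group 4 is adjusted for S24 and Group 1 for S0, d4 tends to drop out of the contrast.

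**Results.** Group 1 versus Group 4 hazard ratio, category covariate, d1 = −0.5:

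| d4 | 1.4 per point: parent category in both | 1.4: Section 8.4 rule | 1.2 per point: parent category in both | 1.2: Section 8.4 rule |
|---|---|---|---|---|
| +1.0 | 0.634 | 0.786 | 0.774 | 0.879 |
| +0.5 | 0.739 | 0.823 | 0.844 | 0.901 |
| 0 | 0.862 | 0.861 | 0.915 | 0.916 |
| −0.5 | 1.000 | 0.888 | 0.996 | 0.934 |

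With d1 = −1.0 at 1.4 per point, the pairs for d4 = +1.0, +0.5, 0 and −0.5 are 0.548 and 0.679, 0.626 and 0.700, 0.735 and 0.732, and 0.865 and 0.769.

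The mechanism is clearest with a continuous score (1.4 per point, d1 = −0.5). As d4 goes from −0.5 to +1.0, the parent-adjusted hazard ratio moves from 1.001 to 0.626. Under the Section 8.4 rule it stays between 0.887 and 0.899. Three coarse categories remove only part of d4, so the category results lie between these extremes.

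**Other inputs.** With SD 1.9, SD of change 1.3, 1.42 per point and 2 years of follow-up, placebo +0.5 and drug −0.5 gave 0.69 becoming 0.80. With no placebo drift the shift was 0.01 to 0.02. Further runs of this kind gave 0.72 becoming 0.82 for the first case, and a near-null 0.98 becoming 0.87 where completers improve.

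**Time origin.** Restarting the clock at LTE entry gave the same hazard ratio as the parent-dose clock in every scenario, with parent duration set equal for all.

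**Scale against sampling error.** The largest category shift above is ln(0.786/0.634) = 0.215. With D deaths split evenly between two groups, the SE of the log hazard ratio is about √(4/D): 0.45, 0.32 and 0.22 for assumed totals of 20, 40 and 80 deaths.

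**The case against.** Item 1 does not itself call for the Week 24 score; that follows from a default. Section 6.1 allows parent-trial baseline values depending on the outcome, item 1 is framed from the start of the parent trial, and Section 8 leaves details to a SAP. The authors may have meant the parent baseline throughout. This stands as a statement of possible intent, but it does not cure the text. The Section 6.1 allowance is permissive and points especially to the active arms, which already use the parent baseline. The Section 8.4 rule is explicit and names its one exemption.

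A reader might infer that the model adjusts away deterioration on placebo and so understates the benefit of early treatment. The documents do not support that. They give no placebo change in score, and LTE entrants are selected: they completed the parent trial without toxicity that ended treatment (Section 4.1) and were not judged non-compliant (Section 4.2). If such subjects improve, the bias reverses.

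A reader might also blame the parent-dose clock. Nobody in the FAS can die before LTE entry, and moving the clock changed nothing in the simulation. Unequal covariate timing is the cause.

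The clinical-worsening model is not a clean precedent for a parent-only covariate, because it also carries an LTE-baseline score for some ex-placebo subjects. Finally, about 370 subjects are expected, the study's main objective is safety, and the simulated shifts are below one standard error at the death counts assumed. That limits the practical weight of the point. The error is nonetheless systematic and avoidable.

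**Conclusion.** The concern holds as a defect in specification: an undefined covariate that the plan's own rule turns into a non-comparable adjustment for Group 1 versus Groups 4 and 3. Group 1 versus Group 2 is sound, since both groups use the parent baseline.

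The direction is conditional. Under the assumed inputs the bias is toward 1 if ex-placebo subjects worsen: about 0.7 to 0.8 for a half-point rise on placebo and a half-point fall on drug at roughly 1.4 per point, and 0.84 to 0.90 at 1.2 per point. It is negligible if they do not change on average. It is toward a spurious benefit if they improve, with a true hazard ratio near 1.00 becoming about 0.87 to 0.93 when both arms improve by half a point. These sizes rest on assumed score distributions, changes and hazard gradients. The asymmetry itself rests only on the text.

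**What to change.** In Section 8.5.2 item 1, specify the parent-trial pre-first-dose REVEAL Lite 2.0 category as the covariate for all four groups. In Section 8.4, add the overall-survival covariate to the exemption now given to the delayed-start analysis. Make the change before any survival comparison is run.

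The cost is one sentence in each place. The parent-baseline score is already required by the MMRM and the clinical-worsening model, so no new data are needed. This change does not touch the LTE-baseline term in the clinical-worsening model, which should be looked at separately.
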